4. STUDY POPULATION

Up to 48 male and female subjects will be enrolled across 3 centers in the United States.

4.1 INCLUSION CRITERIA

Each subject must meet all of the following criteria to be enrolled in this study:

1. The subject is male or female 18 to 79 years of age, inclusive.
2. The subject has a BMI of 19 to 40 kg/m², inclusive, at screening.
3. Females of childbearing potential must practice a highly effective method of contraception throughout the study period and for 1 month after treatment discontinuation. Highly effective methods are defined as those that can achieve a failure rate of less than 1% per year when used consistently and correctly. Such methods, in accordance with the recommendations of the Clinical Trial Facilitation Group Working Group on Contraception include: hormonal contraception associated with inhibition of ovulation, intrauterine device, intrauterine hormonal-releasing system, bilateral tubal occlusion, vasectomized partner, and sexual abstinence. All female subjects must have a negative pregnancy test at screening and before the first dose of study drug.
4. Male subjects with female partners of childbearing potential must be vasectomized, be willing to use an acceptable method of birth control, or practice abstinence during the study.
5. The subject has a resting pulse rate of ≥ 40 and < 100 beats per minute with no clinically significant deviation as judged by the investigator.
6. The subject has a QT interval corrected for heart rate using Fridericia's formula (QTcF) of < 500 msec.
7. The subject agrees to comply with all protocol requirements.
8. The subject is able to provide written informed consent.

Additional Inclusion Criteria for Healthy Subjects Only (Cohort D):

9. The subject has normal hepatic function.

10. The subject has a resting blood pressure of 90 to 150 mm Hg (systolic) and 50 to 100 mm Hg (diastolic).
11. The subject is judged by the investigator to be in good general health, as determined by medical history, clinical laboratory assessments, vital sign measurements, 12-lead electrocardiogram (ECG) results, and physical examination findings.

Additional Inclusion Criteria for Subjects With Hepatic Impairment Only (Cohorts A, B, and C):

12. The subject has cirrhosis with evidence of impaired liver function. The etiology of the cirrhosis may be alcoholic, autoimmune, nonalcoholic steatohepatitis, or chronic viral hepatitis type B or C.
13. The subject has chronic (more than 6 months) and stable hepatic impairment (ie, no acute episodes of illness within 30 days before screening due to deterioration of hepatic function) as assessed by a Child-Pugh classification score of mild (5 to 6 points), moderate (7 to 9 points), or severe (10 to 15 points).
14. The subject has a resting blood pressure of 90 to 155 mm Hg (systolic) and 50 to 100 mm Hg (diastolic).
15. The subject is judged by the investigator to be in good general health, as determined by medical history, clinical laboratory assessments, vital sign measurements, 12-lead ECG results, and physical examination findings, except for findings that, as judged by the investigator, are consistent with the subject's hepatic impairment or other stable concomitant medical conditions.

4.2 EXCLUSION CRITERIA

Subjects meeting any of the following criteria will be excluded from the study:

1. The subject has a history or clinical manifestations of a significant neurological, renal, cardiovascular, gastrointestinal, pulmonary, hematologic, immunologic, or psychiatric disease that would preclude study participation, as judged by the investigator.
2. The subject has a positive test result for human immunodeficiency virus type 1 or 2 antibodies at screening.
3. The subject has a history of drug abuse within 3 months before screening.

4. The subject has a history of alcoholism within 3 months before screening, or excessive alcohol consumption (regular alcohol intake >15 units per week) (1 unit is equal to approximately ½ pint [200 mL] of beer, 1 small glass [100 mL] of wine, or 1 measure [25 mL] of spirits).
5. The subject smokes >10 cigarettes daily and is unwilling to reduce to ≤5 daily from the time of screening through the last PK sample.
6. The subject is unable or unwilling to abstain from alcohol, caffeine, xanthine-containing beverages or food (eg, coffee, tea, chocolate, and caffeinated sodas, colas), grapefruit, grapefruit juice, Seville oranges, or products containing any of these, from 48 hours prior to study drug dosing until discharge.
7. The subject is involved in strenuous activity or contact sports within 24 hours of the first dose of study drug or during the study.
8. The subject has donated blood or blood products >450 mL within 3 months before the first dose of study drug.
9. The subject has a presence or history of relevant drug and/or food allergies (ie, allergy to aramchol, cholic acid, or any excipients, or any significant food allergy).
10. The subject has received study drug in another investigational study within 30 days of dosing.
11. In the opinion of the investigator, the subject is not suitable for entry into the study.

Additional Exclusion Criteria for Healthy Subjects Only (Cohort D):

12. The subject has clinically significant findings at screening including history, physical examination, ECG, or laboratory values.
13. The subject has used an herbal remedy (including St John's wort) known to interfere with liver enzymes during the 28 days before dosing with the study drug.
14. The subject has a past history of surgery or a medical condition that might affect absorption of medicines (hernia repair is acceptable).
15. The subject has a positive test result for hepatitis B surface antigen or antibodies to hepatitis C virus.

16. The subject has used any prescription (excluding hormonal birth control and hormone replacement therapy) or over-the-counter medications (except paracetamol [up to 2 grams per day]), including herbal or nutritional supplements, within 14 days before the first dose of study drug and throughout the study.
17. The subject has a positive test result for drugs of abuse or alcohol at screening or before the first dose of study drug.

Additional Exclusion Criteria for Subjects With Hepatic Impairment Only (Cohorts A, B, and C):

18. The subject has a current >Grade 1 (mild) encephalopathy. Subjects with a history of Grade 3 or 4 encephalopathy that have responded to treatment with medicines such as lactulose, rifaximin, or neomycin may be included with the subject receiving the point score for Grade 3 or 4 encephalopathy.
19. The subject has clinically demonstrable massive tense ascites. Subjects with a history of moderate or severe ascites that have responded to diuretics may be included with the subject receiving the higher score.
20. The subject has esophageal varices that have caused hemorrhage within a period of 8 weeks prior to dosing or are considered of high risk for hemorrhage.
21. The subject has the following types of liver disease: primary biliary cirrhosis, sclerosing cholangitis, hepatocellular carcinoma, cardiac cirrhosis, hemochromatosis, Wilson's disease, other genetic causes of liver disease.
22. The subject has clinically significant impairment of renal function (eCLcr <45 mL/min) as calculated by the Cockcroft-Gault equation.
23. The subject has a hemoglobin <8.5 mg/dL or platelets <30,000/ μ L.
24. The subject has fluctuating or rapidly deteriorating hepatic function, as indicated by recent history or worsening of clinical (ie, abdominal pain, nausea, vomiting, anorexia, or fever) and/or laboratory signs of hepatic impairment, as judged by the investigator.
25. The subject has evidence of acute viral hepatitis within 30 days before dosing with study drug.
26. The subject has evidence of hepatorenal syndrome.

27. The subject has used any prescription (excluding hormonal birth control and hormone replacement therapy) or over-the-counter medications, including herbal or nutritional supplements, within 14 days before the first dose of study drug and throughout the study, except those essential for the management of hepatic impairment or the treatment of stable concomitant medical conditions, as judged by the investigator. The dose of an approved medication must remain stable from 7 days before study drug dosing and throughout the study.
28. The subject has a positive test result for drugs of abuse (except positive test results associated with prescription medications that have been reviewed and approved by the investigator) at screening or before the first dose of study drug.

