6.2.2 Clinical Laboratory Testing

Clinical laboratory tests will be performed by the clinical sites' local laboratories. Blood and urine samples will be collected and prepared using standard procedures.

Repeat clinical laboratory tests may be performed at the discretion of the investigator, if necessary, to evaluate inclusion and exclusion criteria or clinical laboratory abnormalities. The clinical laboratory that will perform the tests will provide the reference ranges for all clinical laboratory parameters. Abnormal clinical laboratory values will be flagged as either high or low (or normal or abnormal) based on the reference ranges for each laboratory parameter.

Single Dose (Part 1):

Clinical laboratory testing will occur at screening; check-in; on Day 4; prior to discharge on Day 8 (healthy subjects) or Day 11 (hepatically impaired subjects); and at EOS.

Multiple Dose (Part 2):

Clinical laboratory testing will occur at screening; check-in; Days 4, 8, and 12; and at EOS.

The following clinical laboratory assessments will be performed for Parts 1 and 2:

Hematology	Absolute neutrophil count and differential, hematocrit, hemoglobin, mean corpuscular hemoglobin, mean corpuscular hemoglobin concentration, leukocyte count and differential (basophils, eosinophils, lymphocytes, monocytes, and neutrophils [absolute and differential]), mean corpuscular volume, platelet count, red blood cell count, and red blood cell distribution width
Coagulation	International normalized ratio, partial thromboplastin time, and prothrombin time
Serum chemistry	Alanine aminotransferase, albumin, alkaline phosphatase, aspartate aminotransferase, bilirubin (total), blood urea nitrogen, calcium, carbon dioxide, chloride, cholesterol (total, high-density lipoprotein, and calculated low-density lipoprotein), creatinine, gamma-glutamyltransferase, globulin, glucose, lactate dehydrogenase, phosphorus, potassium, sodium, total protein, triglycerides, and uric acid
Urinalysis	Bilirubin, color, glucose, ketones, leukocyte esterase, reflex microscopy (performed if dipstick is positive for protein or the blood value is 1+ or greater; and includes bacteria, casts, crystals, epithelial cells, red blood cells, and white blood cells), nitrites, occult blood, pH, protein, specific gravity, turbidity, and urobilinogen
Serology	Hepatitis B surface antigen, hepatitis C virus antibody, and human immunodeficiency virus antibody types 1 and 2 (screening only)

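### The hemoglobin limit in exclusion criterion 23 is printed in mg/dL, so it can exclude no one and hepatically impaired subjects have no working numeric hemoglobin limit

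*Combined protocol and SAP*

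**What the plan says.** Section 4.2 of the protocol lists additional exclusion criteria for hepatically impaired subjects (Cohorts A, B and C). Criterion 23 is one of them: "The subject has a hemoglobin <8.5 mg/dL or platelets <30,000" per microliter. The synopsis repeats it with the same number and unit.

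Other text bearing on a low hemoglobin:

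- **Section 6.2.2** includes hemoglobin in the hematology panel but gives neither a unit nor a limit. It also states: "Clinical laboratory tests will be performed by the clinical sites' local laboratories".
- **Exclusion 1** covers significant hematologic disease, but only disease "that would preclude study participation, as judged by the investigator".
- **Exclusion 11** is a general bar: "In the opinion of the investigator, the subject is not suitable for entry into the study".
- **Inclusion 15** asks for good general health, "except for findings that, as judged by the investigator, are consistent with the" subject's hepatic impairment or other stable conditions.
- **Section 4** says that subjects "will be enrolled across 3 centers in the United States".

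**The concern.** Criterion 23 has two halves joined by *or*. The hemoglobin half is written as a numeric entry limit, but the printed unit puts that limit where no subject can fall below it. Read literally, it does nothing.

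What is lost is the uniform, auditable number, not every protection against enrolling an anemic subject. The remaining criteria rest on judgement, and inclusion 15 makes an exception for findings consistent with liver disease, where an investigator might well place anemia. A site that follows the text applies no hemoglobin limit. A site that silently substitutes another unit applies a limit the protocol does not state. The three sites could therefore treat the same subject differently, and a monitor has no usable number to cite. This matters because Section 9.2.3.2.2 allows a breach of an eligibility criterion to count as an important deviation.

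The limit is also relevant to the study procedures: Section 6 allows up to 500 mL of blood per subject, and exclusion 8 bars recent donors of more than 450 mL.

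**Working it through.** **Inputs**

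- Printed hemoglobin limit: 8.5 mg/dL (Section 4.2 and synopsis, criterion 23).
- Planned sizes in Part 1: 8 each in Cohorts A, B and C, with Cohort A opening only on evidence of reduced clearance in Cohort B (Section 3).
- The documents give no hemoglobin range. I assumed 3 to 15 g/dL.

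**1. Conversion.** 1 g = 1000 mg, so 8.5 mg/dL ÷ 1000 = 0.0085 g/dL.

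**2. The printed rule applied to the assumed range.** A subject is excluded if hemoglobin in mg/dL is below 8.5.

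| Hemoglobin (g/dL) | In mg/dL | Multiple of printed limit | Excluded as printed? |
|---|---|---|---|
| 3 | 3,000 | 3,000 ÷ 8.5 ≈ 353 | No |
| 5 | 5,000 | 5,000 ÷ 8.5 ≈ 588 | No |
| 7 | 7,000 | 7,000 ÷ 8.5 ≈ 824 | No |
| 10 | 10,000 | 10,000 ÷ 8.5 ≈ 1,176 | No |
| 15 | 15,000 | 15,000 ÷ 8.5 ≈ 1,765 | No |

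Even the lowest assumed value is about 353 times the printed limit, so the result does not depend on the range chosen.

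**3. Size of the slip, if it is one of unit only.** If g/dL was intended (an assumption), 8.5 ÷ 0.0085 = 1000-fold.

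**4. Is the unit corrected elsewhere?** No. The synopsis and Section 4.2 agree with each other, which also makes an artefact of text extraction unlikely. Table 5-1 gives bilirubin in mg/dL and albumin in g/dL. Both units are thus in use, which makes a slip plausible but does not establish what was meant.

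**5. Does another criterion supply a number?** No. Exclusions 1, 11 and 24 and inclusion 15 rest on judgement. Exclusion 20 concerns only esophageal varices with recent bleeding or a high risk of it. Item 2 of Section 4.3 permits repeat testing but sets no limit.

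**6. The platelet half.** The limit "platelets <30,000" per microliter has a workable unit and operates on its own.

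**7. Places covered in Part 1.** Cohorts B and C: 8 + 8 = 16. With Cohort A: 16 + 8 = 24. Part 2 plans at least 8 further impaired subjects (Section 7.1). The heading above criterion 23 names only Cohorts A, B and C, so I have not counted them.

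**The case against.** The strongest reply is that the error announces itself. A limit of 0.0085 g/dL is physically impossible, so any site would see a misprint, and if all sites read it the same way a uniform limit applies in practice. Nothing in the documents shows sites acting differently. Use of local laboratories adds little, since a fixed cut-off does not depend on a laboratory's reference range. Low values would also not go unseen: Section 6.2.2 flags abnormal results, Section 6.2 has the investigator judge their clinical significance, and exclusion 24 covers worsening laboratory signs of hepatic impairment. The count of 16 or 24 is not a count of subjects affected, which could be zero. On this view the point is editorial.

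Much of this stands. The practical harm is probably small, divergence between sites is a possibility and not an observation, and the count describes coverage only. The local-laboratory point is background and carries no weight in the conclusion.

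It does not remove the defect. Eligibility is applied and audited against the written text, and the text states a limit that cannot operate. Flagging and clinical judgement do not replace the number that the protocol set out to give. The documents also do not say what was intended, so each site would have to infer it.

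**Conclusion.** The concern holds. As printed, the hemoglobin half of criterion 23 excludes no subject, and no other provision sets a numeric hemoglobin limit for hepatically impaired subjects. The defect covers 16 planned places in Part 1, or 24 if Cohort A opens; how many subjects it would affect is unknown. The 1000-fold figure applies only if g/dL was intended. That the limb is inoperative rests on the unit conversion and on human hemoglobin lying far above 0.0085 g/dL.

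The platelet half, the sample size and the pharmacokinetic analyses are unaffected. Because this is an operative eligibility limit with a safety purpose, it should be fixed, although many sites would probably spot the misprint.

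**What to change.** The sponsor should confirm the intended unit and value of the hemoglobin limit in criterion 23, then correct Section 4.2 and the synopsis together in the next protocol version. Any eligibility checklist or data-entry check that uses the criterion should follow the corrected text. While making the change, the sponsor could also state whether the criterion applies to the impaired subjects in Part 2.

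The cost is a wording correction in two places once the unit and value are confirmed. The design, sample size and analysis do not change.

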4.3 OTHER SCREENING CONSIDERATIONS

1. For inclusion and Child-Pugh categorization, clinical laboratory test results that are deemed inconsistent with the usual stage of hepatic impairment may be repeated.
2. For eligibility purposes, abnormal vital sign, clinical laboratory test, or ECG results may be repeated if an abnormal result is observed at the initial reading.
3. In the event that the participation of a subject in the study is delayed and some screening procedures are performed outside of the prescribed screening window, outdated screening procedures may be repeated.
4. Subjects who do not qualify based on a reversible medical condition or mild intercurrent illness may be reevaluated after further testing/examination or rescreened after the condition is resolved.
5. Subjects are categorized by hepatic impairment at screening. If the Child-Pugh classification scores change on Day -1 due to a change in clinical status or clinical laboratory test results that are not clinically significant, the subject will keep their original score.

4.4 WITHDRAWAL OF SUBJECTS FROM THE STUDY

4.4.1 Reasons for Withdrawal

Subjects can withdraw consent and discontinue from the study at any time, for any reason, without prejudice to further treatment.

The investigator may withdraw a subject from the study if the subject:

1. Is noncompliant with the protocol;
2. Experiences an SAE or intolerable AE(s) that in the investigator's opinion requires withdrawal from the study;
3. Has laboratory safety assessments that reveal clinically significant hematological or biochemical changes from baseline values;
4. Develops, during the course of the study, symptoms or conditions listed in the exclusion criteria;
5. Requires a medication prohibited by the protocol; or
6. Requests an early discontinuation for any reason.

The investigator can also withdraw a subject upon the request of the sponsor, or if the sponsor terminates the study. Upon occurrence of an intolerable SAE or intolerable AE, the investigator will confer with the sponsor. If a subject is discontinued because of an AE, the event will be followed until it is resolved, stable, or judged by the investigator to be not clinically significant.

4.4.2 Handling of Withdrawals

Subjects are free to withdraw from the study at any time upon request. Subject participation in the study may be stopped at any time at the discretion of the investigator or at the request of the sponsor.

When a subject withdraws from the study, the reason(s) for withdrawal shall be recorded by the investigator on the relevant page in the electronic case report form (eCRF). Whenever possible, any subject who withdraws from the study prematurely will undergo all EOS assessments. Any subject who fails to return for final assessments will be contacted by the site in an attempt to have them comply with the protocol. The status of subjects who fail to complete final assessments will be documented in the eCRF.

4.4.3 Replacements

At the discretion of the investigator, and after consultation with the medical monitor and sponsor, any subject who withdraws before completing the study may be replaced to retain the target of 6 evaluable subjects based on clinical considerations. Any replacement subject will be assigned to receive the same treatment as the subject he or she is replacing.

5. STUDY TREATMENTS

5.1 TREATMENTS ADMINISTERED

All doses of study drug will be administered by mouth with 240 mL of room temperature water. During the study, subjects may consume water on an ad libitum basis.

Hepatically impaired subjects will receive a diet standardized for hepatic impairment and healthy control subjects will receive a similar diet. Subjects should receive these meals at the same time during each part of the study.

Single Dose (Part 1):

On Day 1, all subjects will receive a single oral dose of 600 mg (2 × 300-mg tablets) aramchol in the morning, after an overnight fast of at least 10 hours and approximately 30 minutes after a standardized breakfast.

Multiple Dose (Part 2):

Starting on Day 1, all subjects will receive an oral dose of aramchol that will not exceed 300 mg twice daily (approximately 12 hours apart) for 11 days and a single AM dose on Day 12 approximately 30 minutes after a standardized meal. The dose may be adjusted to give lower exposure depending on the review of available data on any reduction in clearance associated with hepatic impairment seen with single doses in Part 1.

5.2 INVESTIGATIONAL PRODUCTS

Aramchol will be supplied as 300-mg tablets.

[REDACTED]

5.2.1 Study Drug Packaging and Storage

The sponsor will provide the investigator and clinical site with adequate quantities of aramchol. The clinical site pharmacy will prepare the study treatments for each subject according to the schedule of events for Parts 1 and 2 (Section 3.1 and Section 3.2, respectively).

All study drugs must be stored according to the labeled instructions in a secure cabinet or room with access restricted to necessary site personnel. The site will be required to keep a temperature log to establish a record of compliance with storage conditions.

5.2.2 Study Drug Accountability

The investigator will maintain accurate records of receipt of all study drugs, including dates of receipt. Accurate records will be kept regarding when and how much study drug is dispensed and used by each subject in the study. Reasons for departure from the expected dispensing regimen must also be recorded. At the completion of the study, and to satisfy regulatory requirements regarding drug accountability, all study drugs will be reconciled and retained or, with approval of the sponsor, destroyed according to applicable regulations.

5.3 METHOD OF ASSIGNING SUBJECTS TO TREATMENT GROUPS

This is a nonrandomized study. At screening, hepatically impaired subjects will be assigned to a study group based on their level of hepatic function according to the Child-Pugh classification system, as shown in Table 5–1. To allocate subjects to the appropriate cohort of hepatic impairment severity, a history of higher severity that has responded to medication will be taken into account. Thus, subjects with a history of Grade 3 or 4 encephalopathy that have responded to treatment with medicines such as lactulose or neomycin may be included with the subject receiving the point score for Grade 3 or 4 encephalopathy. Similarly, subjects with a history of moderate or severe ascites that have responded to diuretics may be included with the subject receiving the higher score.

Table 5–1 Child-Pugh Classification System

Points ^(a)	Bilirubin (mg/dL)	Albumin (g/dL)	Prothrombin Time (seconds prolonged)	Encephalopathy (grade) ^(b)	Ascites (grade)
1	<2.0	>3.5	<4	None (Grade 0)	Absent
2	2.0 to 3.0	2.8 to 3.5	4 to 6	1 or 2	Slight
3	>3.0	<2.8	>6	3 or 4 or subjects receiving medication(s) to prevent encephalopathy	Moderate or severe subjects on medication(s) to control ascites

Abbreviation: INR, international normalized ratio.

^(a) For each category (bilirubin, albumin, prothrombin time or INR, encephalopathy grade, and ascites), points are assigned based on the subject’s condition and the criterion met. The Child-Pugh class is assigned based on the sum of these points as follows: Child-Pugh Class A or mild hepatic impairment if the sum is 5 or 6 points; Child-Pugh Class B or moderate hepatic impairment if the sum is 7 to 9 points; and Child-Pugh Class C or severe hepatic impairment if the sum is 10 to 15 points.

^(b) Grade 0: normal consciousness, personality, neurological examination, electroencephalogram.
 Grade 1: restless, sleep disturbed, irritable/agitated, tremor, impaired handwriting, 5 count-per-second waves.
 Grade 2: lethargic, time-disoriented, inappropriate, asterixis, ataxia, slow triphasic waves.
 Grade 3: somnolent, stuporous, place-disoriented, hyperactive reflexes, rigidity, slower waves.
 Grade 4: unarousable coma, no personality/behavior, decerebrate, slow 2-3 count-per-second delta activity.

Hepatically impaired subjects (Cohorts A, B, and C) will be enrolled as they become eligible and receive their allocated subject numbers in the order in which they are enrolled into their respective cohorts.

